# 10.5 Confidentiality and Publication of Study Results

### 10.5.1 General

All data and information supplied by or on behalf of the Sponsor or otherwise acquired or obtained by any Research Institution, the PI and other investigators ("Recipients") in any manner, in connection with or in performance of this study, is considered "Confidential Information." This Confidential Information includes, but is not limited to, the IB, this protocol and any information relating thereto, eCRFs and other scientific data, information relating to Sponsor's Investigational Product and treatment methodology and information relating to Sponsor's (or its affiliates") commercial, technical and financial information, research technology, products, inventions, trade secrets and research and development. The results produced in performance of the study and any data, information or other material collected or generated in the course of performing the study shall be promptly disclosed to Sponsor in full in writing and are also considered Confidential Information. This Confidential Information shall be the sole property of the Sponsor.

Except for Publishable Results (defined below) to the extent it may be published under Section 10.5.2, throughout the duration of the study and after its completion, Recipients shall

- (i) not disclose Confidential Information to others without the written consent of the Sponsor, except to those of its employees who have a need to know the Confidential Information in order to enable Recipients' to fulfil their obligations hereunder, and where such employees are bound by written contractual obligations covering Confidential Information that are no less restrictive or protective than those contained herein, *provided that* Recipients shall remain liable for any disclosure or use of Confidential Information by such employees;
- (ii) use the same degree of care to preserve confidentiality of Confidential Information as they use for their own information of like nature, which shall not be less than reasonable degree of care; and
- (iii) not use Confidential Information for any purpose except in the performance of this study. Promptly at Sponsor's request, or upon completion of the study, Recipients will discontinue use and return to Sponsor or destroy, in accordance with Sponsor's instructions, all copies or other manifestations of Confidential Information that may be in their possession or control, except to the extent expressly required hereunder and to comply with Applicable Laws (defined below).

Should a Recipient be required to disclose Confidential Information pursuant to law, regulation, judicial or administrative order or request by a governmental or other entity authorised by law to make such request, Recipient shall (i) promptly notify Sponsor prior to such disclosure,

agalin A subsidiary of Bio	OLINE AX	PRIVILEGED & CONFIDENTIAL
Investigational Product: AGI-134	A Phase I/IIa, multicentre, two-parts, open label study designed to evaluate the safety and tolerability of escalating	Protocol No. AGI-134.FIM.101
Phase: I/IIa	doses of AGI-134 in unresectable/metastatic solid tumours.	Version 6.1 31 May 2021

(ii) cooperate with Sponsor and provide assistance in seeking a protective order or other suitable protection with respect to the Confidential Information, and (iii) only disclose such Confidential Information to the extent pursuant to said law, regulation, judicial or administrative order, or request by a governmental or other authorised entity.

At the subject's request, medical information may be given to his or her personal physician or other appropriate medical personnel responsible for his or her welfare. The personal physician will be notified by site personnel of subject participation in the study.

#### 10.5.2 Published Data

The original eCRFs and the data generated from the eCRFs or otherwise obtained during the study under this study protocol will become the property of the Sponsor. Publication of the results of this study ("Publishable Results") in an appropriate peer-reviewed journal after the conclusion of the study ("Publication") made be made as provided herein. Publication must be undertaken in a responsible and ethical manner, taking into account relevant external standards regarding the manner and content of scientific, technical and medical publications and in subject to applicable laws, rules, regulations, policies and guidelines ("Applicable Laws"). Authorship will be determined by mutual agreement between Sponsor and PI. Sponsor shall be mentioned in all Publications unless contrary instruction is given by Sponsor. Review and comment by Sponsor authorised personnel on draft abstracts and manuscripts for Publication or presentation is required prior to publication or presentation. Authors shall submit a copy of any abstracts, manuscripts or other material proposed for publication or presentation ("Draft Publications") to the Sponsor for its approval no fewer than sixty (60) days prior to the intended date of submission of such Draft Publications to any journal, publisher, and/or third party. The Sponsor has the right, at its discretion (a) to evaluate Draft Publications for accuracy and concurrence regarding data, evaluations, and conclusions, (b) to provide an opportunity for Sponsor to share with the Investigator(s) any new or unpublished information of which he or she may be unaware, (c) to ensure that no Confidential Information or other Sponsor proprietary information is being utilised and has been included, and (d) evaluate Draft Publications to determine if patent applications need to be filed on any information disclosed therein.

If the Sponsor determines that such Draft Publication contains Confidential Information or could otherwise be detrimental to Sponsor's intellectual property interest or have other adverse effects on its business, and notifies PI of its determination, the PI, Research Institutions and other Investigators/authors shall remove such Confidential Information from the Draft Publication or at Sponsor's election, modify it to remove language that is detrimental to Sponsor's intellectual property or other interests, and refrain from submitting such Draft Publication to a journal, publisher and/or other third party for additional ninety (90) days from Sponsor's notification to allow for filing of patent applications or the taking of such other measures as Sponsor deems appropriate to establish, preserve and protect its intellectual property or other interests. Principal Investigator, other Investigators and Research Institutions further agree to redact or modify those sections of the draft Publication which the Sponsor in good faith determines falls within (a) to (d) above.

agalin A subsidiary of BIO		PRIVILEGED & CONFIDENTIAL
Investigational Product: AGI-134	designed to evaluate the safety and tolerability of escalating	Protocol No. AGI-134.FIM.101
Phase: I/IIa	doses of AGI-134 in unresectable/metastatic solid tumours.	Version 6.1 31 May 2021

# 12 APPENDICES

APPENDIX A: Schedule of Assessments

agalin A subsidiary of BIG		PRIVILEGED & CONFIDENTIAL
Investigational Product: AGI-134	A Phase I/IIa, multicentre, two-parts, open label study designed to evaluate the safety and tolerability of escalating doses of AGI-134 in unresectable/metastatic solid tumours.	Protocol No. AGI-134.FIM.101
Phase: I/IIa		Version 6.1 31 May 2021

Table 6: Schedule of Assessment - Part 1: Accelerated Dose Escalation of AGI-134

Study Period:	Screening Phase	Baseline Assessments					3-	We	ek (	Cyc	les				9-Week F.U Cycles	Termination Visit	Long-Term Follow-up
Treatment Cycle:	Screening (Visit 1)	Pre-Dose	Cycle 1		1	C	Cycle 2		С	Cycle 3			cle	4	Weeks 18, 27, 36 & 45	Week 54 or early Termination	Survival Follow-up call
Days from injection (Safety assessment follow-up)	-28	0	1	8	15	1	8	15	1	8	15	1	8	15			
Scheduling Window (Days) unless specified otherwise	-28 to 0	-3 to 1 Pre- dose		+3			±3			±3			±3		±3	±3	Every 9 weeks (±7 days)
Informed Consent	X																
Inclusion/Exclusion Criteria	X	X 								Г							
Demographics and Medical History	X																
Disease history (including genetic information, dMMR/MSI and Tumour Mutational status)	Х																
Disease treatment history	X																
Prior and Concomitant Medication Review	X	X	X	X	X	X	X	X	X	X	X	X	X	X	Х	X	
Review Adverse Events	X	X	X	X	X	X	X	X	Х	X	X	X	X	X	X	X	
12-Lead Electrocardiogram (ECG) local reading	X		X 			X 			X 			X 				X	
12-Lead Electrocardiogram (ECG) central reading			X 									X3					
Full Physical Examination	X					Ī				Ī	1					X	

agalin A subsidiary of Bio		PRIVILEGED & CONFIDENTIAL
Investigational Product: AGI-134	A Phase I/IIa, multicentre, two-parts, open label study designed to evaluate the safety and tolerability of escalating doses of AGI-134 in unresectable/metastatic solid tumours.	Protocol No. AGI-134.FIM.101
Phase: I/IIa		Version 6.1 31 May 2021

Study Period:	Screening Phase	Baseline Assessments					3-	We	ek (	Сус	les				9-Week F.U Cycles	Termination Visit	Long-Term Follow-up
Treatment Cycle:	Screening (Visit 1)	Pre-Dose	Cycle 1			C	Cycle 2			Cycle 3			ycle	4	Weeks 18, 27, 36 & 45	Week 54 or early Termination	Survival Follow-up call
Days from injection (Safety assessment follow-up)	-28		1	8	15	1	8	15	1	8	15	1	8	15			
Scheduling Window (Days) unless specified otherwise	-28 to 0	-3 to 1 Pre- dose		+3			±3			±3			±3		±3	±3	Every 9 weeks (±7 days)
Symptoms Directed Physical Examination		X	X 	X	X	X 	X	X	X 	X	X	X 	X	X			
Examination of injection sites			$X^5$	X	X	$X^5$	X	X	X 	X	X	X 	Х	X	X	X	
Vital Signs (blood pressures, pulse rate, O 2 sat., oral temperature (°C), respiratory rate)	Х		X 	X	X	X8	X	Х	X8	X	X	X 	X	Х		X	
Weight	X															X	
Height	X												T				
ECOG performance status	X		Х			X			X			X	T		X	X	
Photography pictures of lesions that are Superficial			X 	Х	Х	X 	X	X	X 	X	X	X 	X	X	X	X	
Review general instructions before study drug administration			X			X			X			X					
AGI-134 administration 			Х			X			Х			X	T				

		PRIVILEGED & CONFIDENTIAL
Investigational Product: AGI-134	A Phase I/IIa, multicentre, two-parts, open label study designed to evaluate the safety and tolerability of escalating doses of AGI-134 in unresectable/metastatic solid tumours.	Protocol No. AGI-134.FIM.101
Phase: I/IIa		Version 6.1 31 May 2021

Study Period:	Screening Phase	Baseline Assessments	3-Week Cycles								es				9-Week F.U Cycles	Termination Visit	Long-Term Follow-up				
Treatment Cycle:	Screening (Visit 1)	Pre-Dose	Cy	cle	1	C	ycle	2	C	ycle	3	Cy	Cycle 4		Cycle 4		Cycle 4		Weeks 18, 27, 36 & 45	Week 54 or early Termination	Survival Follow-up call
Days from injection (Safety assessment follow-up)	-28	0	1	8	15	1	8	15	1	8	15	1	8	15							
Scheduling Window (Days) unless specified otherwise	-28 to 0	-3 to 1 Pre- dose	8	+3			±3			±3			±3		±3	±3	Every 9 weeks (±7 days)				
Local Laboratory 							u														
Pregnancy Test – Serum or Urine 	X	X				X						X				X					
FSH screening for women who reported menopause less than two years.	X																				
Disease markers according to subject's disease	X					X						X									
HPV status for HNSCC 	X		П																		
PT/INR and aPTT	X	X				X			Х			X									
CBC with Differential	X	X	$X^{13}$	X	X	X			X			X				X					
Biochemistry Panel	X	X	$X^{13}$	X	X	X			X			X				X					
T3, free T4, and TSH	X					X						X				X					
HIV, HBV and HCV serology	X																				
Urinalysis	X	X				X						X									

agalin A subsidiary of BIG		PRIVILEGED & CONFIDENTIAL
Investigational Product: AGI-134	A Phase I/IIa, multicentre, two-parts, open label study designed to evaluate the safety and tolerability of escalating doses of AGI-134 in unresectable/metastatic solid tumours.	Protocol No. AGI-134.FIM.101
Phase: I/IIa		Version 6.1 31 May 2021

Study Period:	Screening Phase	Baseline Assessments	3-Week Cycles								9-Week F.U Cycles	Termination Visit	Long-Term Follow-up				
Treatment Cycle:	Screening (Visit 1)	Pre-Dose	C	ycle	1	C	ycle	2	C	cle	3	Cy	Cycle 4		Weeks 18, 27, 36 & 45	Week 54 or early Termination	Survival Follow-up call
Days from injection (Safety assessment follow-up)	-28	0	1	8	15	1	8	15	1	8	15	1	8	15			
Scheduling Window (Days) unless specified otherwise	-28 to 0	-3 to 1 Pre- dose		+3			±3			±3		H	±3		±3	±3	Every 9 weeks (±7 days)
Central Laboratory																	
Blood for Anti-Gal Antibodies complement activation and cytokines		X								X 						X	
Blood for PBMC Isolation		X								$X^{14}$					X 	X	
Blood for Anti-Gal IgE	X								X 								
HLA haplotyping		X															
Blood for immunophenotyping by FACS		X								X 					X 	X	
Blood for RNA/ DNA		X								X 					X 	b	
Blood for PK		2	X15			X 			$X^{16}$			$X^{14,15}$				9	
Biopsies	100	×															
Biopsy of injected lesion9		X 								$X^{18}$					X 		
Biopsy for un-injected lesion9		X 								$X^{18}$					X 		
Disease Assessment			3.00												*		·
Tumour Imaging 	X										X				X	X	
RECIST 1.1 assessment	X										$X^4$				X	X	

agalin A subsidiary of BIG		PRIVILEGED & CONFIDENTIAL
Investigational Product: AGI-134	A Phase I/IIa, multicentre, two-parts, open label study designed to evaluate the safety and tolerability of escalating doses of AGI-134 in unresectable/metastatic solid tumours.	Protocol No. AGI-134.FIM.101
Phase: I/IIa		Version 6.1 31 May 2021

Study Period:	Screening Phase	Baseline Assessments		3-Week Cycles							es				9-Week F.U Cycles	Termination Visit	Long-Term Follow-up
Treatment Cycle:	Screening (Visit 1)	Pre-Dose	Cycle 1		Cycle 2		Cycle 3		Cycle 4		4	Weeks 18, 27, 36 & 45	Week 54 or early Termination	Survival Follow-up call			
Days from injection (Safety assessment follow-up)			8	15	1	8	15	1	8	15	1	8	15				
Scheduling Window (Days) unless specified otherwise	-28 to 0	-3 to 1 Pre- dose		+3			±3		3	±3 ±3			±3	±3	Every 9 weeks (±7 days)		
Post-study Anti-Cancer Therapy Status																X 	Х
Survival Status																X 	X

- Inclusion/Exclusion Criteria should be re-assessed at Baseline prior to final eligibility confirmation
- A 12-lead ECG will be recorded at each cycle (1-4) prior to AGI-134 administration (up to 1 hour) and 2 hours after dose (±30 minutes). In cycle 1 and 4 when a Holter device is connected a printout should be extracted from the device at the appropriate timepoints

  In Cycle 1 and 4 a 12-lead ECG holter recording device will be connected to the subject 1-2 hours prior to AGI-134 administration and record ECG consecutively for at least 24 hours after AGI-134 administration
- Pre-dose only
- To be performed up to 1 hour prior to AGI-134 administrations and 1 hour post AGI-134 administration. On Cycle 1 and Cycle 4, to be performed also 72 hours post AGI-134 administration

- Vital signs will be collected up to 1 hour pre-dose and 0.5, 1, 24, 36, 48 and 72 hrs post AGI-134 administration
  Vital signs will be collected prior to AGI-134 administration and 2 hours post dose
  Refer to "Administration AGI-134 and Tumour Biopsy Procedures in Study AGI-134.FIM.101" for detailed information
- 10. All laboratory assessment should be performed before investigation product administration unless otherwise specified. Coagulation test results should be available before AGI-134 injections and biopsies
- Pregnancy test in Screening and Termination must be serum. At other visits should be a urine test
   HPV status assessment should be performed at local lab in case no available status from the time of HNSCC diagnosis
   To be drawn 72 hours post AGI-134 administration

- 14. To be drawn on Cycle 3, during week 8 (concomitant with biopsies)
  15. To be drawn up to 1 hour prior to AGI-134 administration and 0.5, 1, 2, 4, 6, 8, 12, 24, 36, 48 and 72 hrs post AGI-134 administration
- 16. To be drawn up to 1 hour prior to AGI-134 administration and 2 hours post dose
  17. The biopsies can be performed on the day of the first dose and up to 3 days prior
- 17. The biopsies can be performed on the day of the first dose and up to 3 days prior18. The biopsies should be performed on Cycle 3, during week 8

agalin A subsidiary of Bio		PRIVILEGED & CONFIDENTIAL
Investigational Product: AGI-134	A Phase I/IIa, multicentre, two-parts, open label study designed to evaluate the safety and tolerability of escalating doses of AGI-134 in unresectable/metastatic solid tumours.	Protocol No. AGI-134.FIM.101
Phase: I/IIa		Version 6.1 31 May 2021

- Optional, on week 27
   CT or MRI (according to Imaging Manual)
   Only for Early Termination visit

agalin A subsidiary of Bio		PRIVILEGED & CONFIDENTIAL
Investigational Product: AGI-134	A Phase I/IIa, multicentre, two-parts, open label study designed to evaluate the safety and tolerability of escalating doses of AGI-134 in unresectable/metastatic solid tumours.	Protocol No. AGI-134.FIM.101
Phase: I/IIa		Version 6.1 31 May 2021

Table 7: Schedule of Assessment - Part 2: AGI-134 at the RP2D

	Screening	Baseline					C	ore Stud	y			Long-Term
	Visit	Visit		Cyc	le 1		Cycle Cycle		Cycle	Visits	Termination	Follow- up
Days	0	0	Day 1	Day 3	Day 8	Day 15	2	3	4		Visit/Early Termination Visit	
Weeks	0	0	1	1	2	3	4-6	7-9	10-12	18, 27, 36 & 45	54	Every 9 weeks
Scheduling Window (Days) unless specified otherwise	-28 to 0	-3 to Day 1 (Pre- dose)	0	±1	+3	+3	±3	±3	±3	±3	±3	±7
Informed Consent	X											
Inclusion/Exclusion Criteria	X	$X^1$										
Demographics and Medical History	X											
Disease history (including genetic information, dMMR/MSI/TMB)	X											
Disease treatment history	X											
Prior and Concomitant Medication Review	X	X	X		X	X	X	X	X	X	X	
Review Adverse Events	X	X	X		X	X	X	X	X	X 	X 	X 
12-Lead Electrocardiogram (ECG) local reading	X		X 				$X^2$	X 	X 		X	
12-Lead Electrocardiogram (ECG) central reading			X³					X 				

agalin A subsidiary of BIC		PRIVILEGED & CONFIDENTIAL
Investigational Product: AGI-134	A Phase I/IIa, multicentre, two-parts, open label study designed to evaluate the safety and tolerability of escalating doses of AGI-134 in unresectable/metastatic solid tumours.	Protocol No. AGI-134.FIM.101
Phase: I/IIa		Version 6.1 31 May 2021

	Screening	Baseline					C	ore Stud	y			Long-Term Follow- up
	Visit	Visit		Cyc	cle 1	***	Cycle	Cycle	Cycle	Visits	Termination	
Days	0	0	Day 1	Day 3	Day 8	Day 15	2	3	4		Visit/Early Termination Visit	
Weeks	0	0	1	1	2	3	4-6	7-9	10-12	18, 27, 36 & 45	54	Every 9 weeks
Scheduling Window (Days) unless specified otherwise	-28 to 0	-3 to Day 1 (Pre- dose)	0	±1	+3	+3	±3	±3	±3	±3	±3	±7
Full Physical Examination	X										X	
Symptoms Directed Physical Examination		X	X 		Х	Х	X 	X 	X 			
Examination of injection sites			X 	$X^6$	X	X	X 	X 	X 	X	X	
Vital Signs (blood pressures, pulse rate, O 2 sat., oral temperature (°C), respiratory rate)	X		X 		Х	Х	X 	X 	X8		X	
Weight	X										X	
Height	X											5
ECOG performance status	X		X				X	X	X	X	X	
Photography of superficial injected and non-injected lesions			X 	X 	X	X	X 	X 	X 	X	X	
Review general instructions before study drug administration			Х				X	X	X			
AGI-134 administration 			X				X	X	X			

agalin A subsidiary of Bio		PRIVILEGED & CONFIDENTIAL
Investigational Product: AGI-134	A Phase I/IIa, multicentre, two-parts, open label study designed to evaluate the safety and tolerability of escalating doses of AGI-134 in unresectable/metastatic solid tumours.	Protocol No. AGI-134.FIM.101
Phase: I/IIa		Version 6.1 31 May 2021

	Screening	Baseline			Long-Term							
	Visit	Visit		Cyc	cle 1	¥11	Cycle	Cycle	Cycle	Visits	Termination	Follow- up
Days	0	0	Day 1	Day 3	Day 8	Day 15	2	3	4		Visit/Early Termination Visit	
Weeks	0	0	1	1	2	3	4-6	7-9	10-12	18, 27, 36 & 45	54	Every 9 weeks
Scheduling Window (Days) unless specified otherwise	-28 to 0	-3 to Day 1 (Pre- dose)	0	±1	+3	+3	±3	±3	±3	±3	±3	±7
Local Laboratory 		<del> </del>	•							 		
Pregnancy Test – Serum or Urine 	X	X					X		X		X	
FSH screening for women who reported menopause less than two years	X											
Disease markers according to subject's disease	X						X		X			
HPV status for relevant indications 	X											
PT/INR and aPTT	X	X					$X^4$	X 	$X^4$			
CBC with Differential	X	X		X	Х	X	X 	X 	$X^4$		X	
Biochemistry Panel	X	X		X	Х	X	X 	X 	$X^4$		X	
T3, free T4, and TSH	X						X		X		X	
HIV, HBV and HCV serology	X											

agalin A subsidiary of B 10	IMUNE LINERX	PRIVILEGED & CONFIDENTIAL
Investigational Product: AGI-134	A Phase I/IIa, multicentre, two-parts, open label study designed to evaluate the safety and tolerability of escalating doses of AGI-134 in unresectable/metastatic solid tumours.	Protocol No. AGI-134.FIM.101
Phase: I/IIa		Version 6.1 31 May 2021

	Screening	Baseline					C	ore Stud	y			Long-Term
	Visit	Visit		Cyc	cle 1	271	Cycle	Cycle	Cycle	Visits	Termination	Follow- up
Days	0	0	Day 1	Day 3	Day 8	Day 15	2	3	4		Visit/Early Termination Visit	
Weeks	0	0	1	1	2	3	4-6	7-9	10-12	18, 27, 36 & 45	54	Every 9 weeks
Scheduling Window (Days) unless specified otherwise	-28 to 0	-3 to Day 1 (Pre- dose)	0	±1	+3	+3	±3	±3	±3	±3	±3	±7
Urinalysis	X	X					X		X			
Central Laboratory 			8	·			>		W			8
Blood for Anti-Gal IgE	X							X 				
CH50			X 									
C5a			X 				X 	X 	X 			
Flow cytometry (FACS)			X 				X 	X 			X	
Cytokines			X 	X				X 				
Anti-Gal antibodies IgG/IgM			X		X		X 	X 	X 		X	
Anti-Gal sub classing			X 				X 	X 	X 		X	
PBMCs isolation + cryopreservation			X 	X			X 	X 			X	
HLA and MHCII haplotyping			X 									
DNA isolation (MSI/dMMR/TMB,WES) blood			X 									

agalin A subsidiary of B 10	IMUNE LINERX	PRIVILEGED & CONFIDENTIAL
Investigational Product: AGI-134	A Phase I/IIa, multicentre, two-parts, open label study designed to evaluate the safety and tolerability of escalating doses of AGI-134 in unresectable/metastatic solid tumours.	Protocol No. AGI-134.FIM.101
Phase: I/IIa		Version 6.1 31 May 2021

	Screening	Baseline					C	ore Study				Long-Term
	CONTRACTOR NO.	Visit	Visit Visit	t Cycle 1		Cycle Cycle Cy	Cycle	Cycle Visits	Termination	Follow- up		
Days		0	Day 1	Day 3	Day 8	Day 15	2 3	3	4		Visit/Early Termination Visit	
Weeks	0	0	1	1	2	3	4-6	7-9	10-12	18, 27, 36 & 45	54	Every 9 weeks
Scheduling Window (Days) unless specified otherwise	-28 to 0	-3 to Day 1 (Pre- dose)	0	±1	+3	+3	±3	±3	±3	±3	±3	±7
TCR Sequencing blood			X 					X 			X	
RNA isolation (Gene expression/sequencing) blood			X 	X				X 			X	
Blood for PK (AGI-134 and metabolites)			X 				X 	X 	X 			
Biopsies 				1				L				
Biopsy of injected lesion	*	X 		X 				X 			X 	
Biopsy for un-injected lesion		X 						X 			X 	7
Disease assessment								.				
Tumour Imaging 	X							X		X	X	
RECIST 1.1 assessment	X							X		X	X	
Post-study Anti-Cancer Therapy Status											X	X
Disease and Survival Status											X	X

agalin A subsidiary of BIG		PRIVILEGED & CONFIDENTIAL
Investigational Product: AGI-134	A Phase I/IIa, multicentre, two-parts, open label study designed to evaluate the safety and tolerability of escalating doses of AGI-134 in unresectable/metastatic solid tumours.	Protocol No. AGI-134.FIM.101
Phase: I/IIa		Version 6.1 31 May 2021

- Inclusion/Exclusion Criteria should be re-assessed at Baseline prior to final eligibility confirmation.
- A 12-lead ECG will be recorded at each cycle (1-4) prior to AGI-134 administration (up to 1 hour) and 2 hours after dose (±30 minutes). In Cycle 1 and 3, when a Holter device is connected, a printout should be extracted from the device at the appropriate timepoints.
- In Cycle 1 and 3, a 12-lead ECG Holter recording device will be connected to the subject 1-2 hours prior to AGI-134 administration and record ECG consecutively for at least 24 hours after 3. AGI-134 administration.
- To be performed up to 1 hour prior and 1 hour post AGI-134 administration
- To be performed 48-72 hours post AGI-134 administration (prior to tumour biopsy if applicable) 6.
- Vital signs will be collected up to 1 hour pre-dose and 0.5, 1, 24, 36, 48 and 72 hrs post AGI-134 administration Vital signs will be collected prior to AGI-134 administration and 2 hours post dose
- AGI-134 should be administered on Day 1 of each Cycle. Refer to "Administration AGI-134 and Tumour Biopsy Procedures in Study AGI-134.FIM.101" for detailed
- All laboratory assessment should be performed before investigational product administration, unless otherwise specified. Pregnancy test in Screening and Termination Visit must be serum. At other visits a urine test. 10.
- 11.
- HPV status assessment should be performed at local lab in case no available status from the time of diagnosis.
- To be drawn pre-dose and 24 hours post AGI-134 administration
- 14. To be drawn pre-dose and at 2,6,12, and 24 hours post AGI-134 administration
- To be drawn pre-dose and at 2 and 6 hours post AGI-134 administrations 15.
- To be drawn up to 1 hour prior to AGI-134 administration and 0.5, 1, 2, 4, 6, 8, 12, 24, 36, 48 and 72 hrs post AGI-134 administration 16.
- To be drawn up to 1 hour prior to AGI-134 administration and 2 hours post dose
- 18. To be drawn 24 hours post AGI-134 administration
- The biopsies can be performed on the day of the first dose and up to 7 days prior AGI-134 Injection Superficial only between  $48h\pm24$  hours post AGI-134 administration 19.
- 20.
- If done on the same day of AGI-134 administration, biopsy should be done prior to injection. If not on the same day, a window of -7 days prior AGI-134 administration is allowed
- In case of Early Termination occurring prior to Cycle 3, every effort must be made to perform biopsies on the ET visit Two biopsies should be taken.
- 23. CT or MRI (according to Imaging Manual) or superficial lesion measurement (depending on to the tumour type). In Cycle 3, to be done between Week 9 and Cycle 4 - Day 1 (before injection of AGI-134).
- AEs will be recorded up to 30 days after the last dose of study drug, and SAEs up to 90 or until the initiation of new anti-cancer therapy, whichever is sooner.
- For detailed time window for sample collection refer to the Laboratory Manual

agalin A subsidiary of BIO	PRIVILEGED & CONFIDENTIAL	
Investigational Product: AGI-134	A Phase I/IIa, multicentre, two-parts, open label study designed to evaluate the safety and tolerability of escalating	Protocol No. AGI-134.FIM.101
Phase: I/IIa		Version 6.1 31 May 2021

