## 5.3 Core Study

The duration of the Core Study will be up to 54 weeks.

AGI-134 administration is divided into cycles (each cycle is 3 weeks long). Each cycle may be extended if additional safety assessment is needed.

AGI-134 is administered for up to 4 cycles. For administration and tissue biopsies information and guidance, please refer to the instructions in the *Administration of AGI-134 and Tumour Biopsy Procedures in Study AGI-134.FIM.101* document.

Visits will be named as follows:

- AGI-134 Administration Visits: Visit Cycle 1-Day 1, Visit Cycle 2-Day 1, Visit Cycle 3-Day 1, Visit Cycle 4-Day1
- Other Visits:
   Visit Cycle 1-Day 3, Visit Cycle 1-Day 8, Visit Cycle 1-Day 15, Visit Week 18,
   Visit Week 27, Visit Week 36, Visit Week 45, Week 54 (Termination)

## 5.3.1 Cycle 1

This visit will begin after completion of the Baseline visit. Treatment initiation may be done on the same day of Baseline visit, but Baseline procedures should be completed prior to investigational product administration. On this day, AGI-134 will be administered. The following activities will be performed during this visit. Details on the specific days for each assessment are presented in the SoA (APPENDIX A).

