- Tumour tissue biopsy will be performed 48 ±24 hrs post AGI-134 administration, from injected lesions only. This biopsy is mandatory for superficial injected lesion and is also requested for deep lesions, unless it is not considered in the best interest for the patient by the PI.

## 5.3.3 Cycle 1 - Day 8 and Day 15

The following procedures will be performed:

- Review of change in concomitant medication
- AE Recordings
- Symptom-directed physical examination
- Examination of injection site
- Photography of superficial injected and non-injected lesions if applicable
- Vital signs (blood pressures, pulse rate, O2 saturation, oral temperature in °C, respiratory rate)
- Blood will be drawn for:
  - CBC with differential
  - Biochemistry panel
  - o Anti-Gal antibodies IgG/IgM (Cycle 1 Day 8 only)

## 5.3.4 Cycles 2, 3 and 4

AGI-134 will be administered on Day 1 of each cycle. The following procedures will be performed during these visits; each assessment should be performed before administration of the investigational product unless otherwise specified. Detailed activities are presented in the SoA (APPENDIX A).

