  - PK of AGI-134 and metabolites: up to 1 hour prior to AGI-134 administration and at 0.5, 1, 2, 4, 6, 8, 12, 24, 36, 48 and 72 hrs post AGI-134 administration.
     For detailed time window for sample collection refer to the Laboratory Manual.
- Biopsies should be performed prior to AGI-134 administration. If not done on the same day of AGI-134 administration, a window of -7 days prior AGI-134 administration is allowed. Two biopsies should be taken:
  - From the tumour lesion to be injected
  - From an un-injected lesion
- Tumour imaging assessment
- RECISTv.1.1 assessment or superficial lesion measurement according to the tumour type will be done on Cycle 3, during Week 9 (before injection of AGI-134 on Cycle 4 - Day 1).

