### 8.2 Statistical Methods

This section briefly describes the statistical methods to be used to analyse the data from the study. A detailed Statistical Analysis Plan (SAP) will present the methods in detail. If the methods of the SAP differ from the methods in this section, the methods of the SAP will prevail.

All measured variables and derived parameters will be listed individually and, if appropriate, summarised using descriptive statistics.

For categorical variables, summary tables will be provided giving sample size, absolute and relative frequency, and 95% confidence interval (CI) for proportions.

For continuous variables, summary tables will be provided giving sample size, arithmetic mean, standard deviation, median, minimum and maximum, appropriate percentiles, and 95% CIs for means.

Statistical test performed will be considered statistically significant if the P-value is less than

The data will be analysed using the SAS ® version

The data will be analysed as described in the SAP.

Analysis will be performed for all subjects in the study, as well as for the pre-defined populations, as follows:

- 1. All patients in Part 1
- 2. All patients in Part 1 and 2

Protocol AGI-134.FIM.101 CONFIDENTIAL Page 72 of 108

agalin A subsidiary of BIO		PRIVILEGED & CONFIDENTIAL
Investigational Product: AGI-134	designed to evaluate the safety and tolerability of escalating	Protocol No. AGI-134.FIM.101
Phase: I/IIa		Version 6.1 31 May 2021

- 3. Part 2 patients from a specific sub-population with histologically confirmed advanced cutaneous metastatic melanoma who:
  - 1. Had only one previous treatment with CIP:
    - a) Anti-PD-1 approved for melanoma, and/or
    - b) Anti-cytotoxic T-lymphocyte-associated protein 4 (CTLA-4) therapy approved for melanoma, and
  - 2. Have remained on prior CPI treatment for at least 4 months or have stopped treatment earlier than that, due to toxicity rather than disease progression.

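### Part 1 sites have two incompatible times for the Cycle 3 biopsies, anti-Gal IgG/IgM and PBMC samples (after dose 3 in Table 6, before dose 3 elsewhere), and a combined Part 1 and 2 summary could mix them

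*Combined protocol and SAP*

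**What the plan says.** **Part 1 schedule.** Table 6 marks the biopsies of the injected and un-injected lesions in the Cycle 3 Day 8 column, with footnote 18: "The biopsies should be performed on Cycle 3, during week 8". The row for anti-Gal antibodies, complement activation and cytokines, and the rows for PBMC, FACS and RNA/DNA, are marked in the same column with footnote 14: "To be drawn on Cycle 3, during week 8 (concomitant with biopsies".

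**Body text.** Section 5.3.4 covers Cycles 2 to 4 without restricting itself to one part. For Cycle 3 it says "Biopsies should be performed prior to AGI-134 administration", allows a window of 7 days before the injection if the biopsies are not done on the dosing day, and lists anti-Gal IgG/IgM and PBMC as pre-dose only. Table 3, also not split by part, gives Cycle 3 pre-dose for tissue TCR sequencing, tissue IHC, anti-Gal IgG/IgM and PBMC.

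**Part 2 schedule.** Table 7 footnote 21 says "If done on the same day of AGI-134 administration, biopsy should be done prior to injection", with the same 7-day window.

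**Analysis.** Section 8.2 lists three populations: Part 1 alone; "All patients in Part 1 and 2"; and a Part 2 cutaneous melanoma sub-population. It defers to a SAP that prevails where the two differ. The document contains no separate SAP text.

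**The concern.** The secondary endpoints in Section 2.2.2 include the immune response to AGI-134, support for its mechanism, and biomarkers. Section 5.12.2 plans biopsies of both the injected and the un-injected lesion at baseline and at Cycle 3, so the Cycle 3 biopsy is the main on-treatment tissue reading. A lesion sampled one to two weeks after a third injection is not the same measurement as one sampled two to three weeks after a second.

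Two things are at stake. A Part 1 site that follows Table 6 and one that follows Section 5.3.4 would take samples with different meanings under the same cycle label. And if results from the two parts are combined, time since dose and number of doses would run together with Part, and hence with dose level, because the lower escalation doses are given by design in Part 1.

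**Working it through.** **Inputs**
- Cycle length is 3 weeks (Section 5.3: "AGI-134 administration is divided into cycles (each cycle is 3 weeks long").
- Dosing is on Day 1 (Section 5.3.4: "AGI-134 will be administered on Day 1 of each cycle").
- Part 1 has up to 24 subjects and Part 2 about 35 (Section 8.1). About 10 of the Part 2 subjects are in the melanoma sub-population (synopsis).

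**Step 1: reproduce the plan's calendar.** Dose day of cycle c = 1 + 21(c - 1), giving Days 1, 22, 43 and 64. Week of day d = floor((d - 1)/7) + 1. Cycle 3 runs from Day 43 to Day 63:
- Day 43: floor(42/7) + 1 = week 7
- Day 63: floor(62/7) + 1 = week 9

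Table 7 also gives Cycle 3 as weeks 7-9. Section 5.3.4 agrees in placing the RECIST assessment, which "will be done on Cycle 3, during Week 9 (before injection of AGI-134 on Cycle 4 - Day 1".

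**Step 2: Part 1 by Table 6.** Week 8 is Days 7 × 7 + 1 = 50 to 7 × 8 = 56. Time since dose 3 is 50 - 43 = 7 to 56 - 43 = 13 days.

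**Step 3: Section 5.3.4 and Table 7 footnote 21.** The biopsy window is Day 43 - 7 = 36 to Day 43, before the injection. Time since dose 2 is 36 - 22 = 14 to 43 - 22 = 21 days.

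| | Table 6 (Part 1) | Section 5.3.4; Table 7 |
|---|---|---|
| Biopsy days | 50-56 | 36-43 |
| Doses received | 3 | 2 |
| Days since last dose | 7-13 | 14-21 |

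The two biopsies are one dose and 50 - 43 = 7 to 56 - 36 = 20 days apart.

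**Step 4: sensitivity to counting.** If weeks are numbered from 0, week 8 is Days 57-63, which is 14-20 days after dose 3. With dose 3 moved by the ±3-day window and week 8 left at Days 50-56, the interval is 50 - 46 = 4 to 56 - 40 = 16 days. None of these puts the Table 6 sample before dose 3.

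**Step 5: which bloods are affected.** I could not read the wording of Table 7 footnote 4, so for pre-dose bloods I rely on Section 5.3.4 and Table 3.
- *Anti-Gal IgG/IgM and PBMC:* pre-dose at Cycle 3 there, week 8 in Table 6. This is a clear before-versus-after conflict.
- *C5a, flow cytometry and cytokines:* both a pre-dose sample and samples 2 to 24 hours after dose 3, against week 8 in Table 6 for its complement, FACS and cytokine rows.
- *Blood RNA:* only 24 hours after dose 3, against week 8 in Table 6.
- *Anti-Gal IgE:* pre-dose in Cycle 3 in both parts, so unaffected.

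**Step 6: share of a combined summary.** Maximum Part 1 size is 4 levels × 6 = 24, which reproduces Section 8.1. The maximum share is 24/(24 + 35) = 24/59 = 41%. Assuming one subject at each of four levels and no expansion, it is 4/(4 + 35) = 4/39 = 10%. About 35 - 10 = 25 Part 2 subjects fall outside the melanoma sub-population and enter a named Section 8.2 population only together with Part 1.

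**The case against.** The strongest answer is that this is a planned difference between parts. Section 5.3.4 itself sends the reader to Appendix A for detail, and Table 6 departs from Table 7 elsewhere: Holter recording and full PK sampling fall at Cycle 4 in Part 1 and Cycle 3 in Part 2. That may be so, but neither Section 5.3.4 nor Table 3 says that it applies to Part 2 only, so the conflict within Part 1 stands.

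A reader might go further and infer that Section 8.2 commits the sponsor to pooling the two timepoints. It does not. It names populations. It gives no rule for combining Cycle 3 biomarker values under one visit label, it lists Part 1 alone as a population, and the synopsis displays results by initial dose level and pools only where applicable. The prevailing SAP may separate the samples, and biopsy guidance is partly delegated to a separate procedures document. Mixing is therefore a risk and not a stated analysis. Nor do the visible methods specify a paired biomarker test or decision rule, so the consequence is descriptive summaries that are hard to interpret, not a demonstrated bias.

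A reader might also infer that all Cycle 3 immune bloods move from before to after dose 3. Step 5 shows that this is clear only for anti-Gal IgG/IgM and PBMC.

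**Conclusion.** The contradiction is real and does not depend on how weeks are counted. For the Cycle 3 biopsies, Part 1 sites are told both Days 50-56 (three doses, 7-13 days after the last) and Days 36-43 (two doses, 14-21 days after the last). Anti-Gal IgG/IgM and PBMC carry the same before-versus-after conflict around dose 3. These intervals assume dosing on nominal days.

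The effect on analysis is conditional. If Section 5.3.4 governs and was followed in Part 1, Table 6 is a drafting error and there is nothing to separate. If Table 6 governs, or sites used both timings, a combined Cycle 3 summary would mix them. The Part 1 share would then lie between about 10% and 41%. The upper figure is a ceiling that needs all four dose levels expanded to six and should not be read as the expected share.

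**What to change.** 1. Reconcile Table 6 footnotes 14 and 18 with Section 5.3.4, Table 3 and Table 7 footnote 21. The sponsor should state which timing applies to Part 1; the documents do not settle it.
2. If the difference between parts is intended, or samples have already been taken at both times, add a sentence to Section 8.2 or the SAP: Cycle 3 biopsy, anti-Gal IgG/IgM and PBMC data are summarised by Part, with doses received and days since last dose shown, and the two timepoints are not pooled. If Part 1 itself holds samples at both times, separate them within Part 1 in the same way.
3. Match the other Cycle 3 bloods (RNA, C5a, flow cytometry, cytokines) on time since dose 3 before combining any of them across parts.

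The cost is footnote corrections, one or two sentences, and fewer subjects in each summary. No added samples or subjects are needed.
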